Study Design: This is an open-label, dose-escalation Phase I clinical study conducted in patients with advanced solid tumors, aiming to evaluate the safety, tolerability, PK/PD characteristics, and preliminary efficacy of CNSI-Fe intratumoral injection in patients with advanced solid tumors.

Study Period: The study includes a screening period, a treatment period (including DLT evaluation period), and a follow-up period.

Screening Period: -28 to -1 days, to confirm that the subjects meet the inclusion criteria and do not meet the exclusion criteria.

Treatment Period (including DLT Evaluation Period): The DLT evaluation period is the first treatment cycle (duration: 21 days). During the DLT evaluation period, all subjects will receive CNSI-Fe intratumoral injection according to the protocol plan (preferentially selecting 1 suitable lesion for injection, tentatively with 1 injection on Day 1; if the corresponding dose of the investigational drug cannot be completed in 1 lesion, other lesions can be injected simultaneously; the dosing regimen may be adjusted by the sponsor and investigator based on the PK characteristics of this study). Safety assessments will be performed on Day 7, Day 14, and Day 21 after the first dose to evaluate DLT.

After the DLT evaluation is completed, subjects who do not experience unacceptable toxicity, if the investigator judges that the benefit of continued treatment outweighs

the risk, will enter the maintenance treatment period. In the maintenance treatment period, subjects will continue to receive one more dose of the investigational drug according to the DLT evaluation period dosing regimen (injection into the same lesion as the DLT evaluation period, tentatively with 1 injection on Day 1, the dosing regimen may be adjusted by the sponsor and investigator based on the PK characteristics of this study), and safety assessments will be performed on Day 7, Day 14, and Day 21 after dosing. Samples will be collected at the predetermined timepoints according to the study flow chart.

Follow-up Period: Safety follow-up until 28 days after the last dose.

Dose Escalation

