The DLT (Dose-Limiting Toxicity) evaluation period is in the first cycle, i.e., within 21 days after the first dose. This stage is tentatively set with 3 dose groups (calculated as Fe^{2+} , 30 mg, 60 mg, 90 mg). If ≥ 2 subjects in the 90 mg group observe DLT, the dose will be reduced to 75 mg for safety and tolerability observation; if the dose is increased to 90 mg and MTD (Maximum Tolerated Dose) is still not reached, the SRC

(Safety Review Committee) will discuss continuing to escalate the dose to 120 mg, 150 mg, or even higher (if MTD is still not reached at 120 mg, the SRC will discuss whether to stop dose escalation or directly proceed to 150 mg or even higher doses).

After 3-6 subjects in each dose group have completed the DLT evaluation, the SRC will evaluate the overall safety of each dose group based on the data obtained and determine whether to continue escalating to the next dose group or to determine the recommended dose for subsequent clinical development.

Enrollment Interval: To fully protect the safety of the subjects, during the dose escalation process, the first subject in each dose group must be dosed at least 3 days after the first dose, and the remaining subjects in that dose group can then start the first dose. The interval for subsequent subjects in the same dose group can be controlled at the discretion of the investigator. The last subject in each dose group must complete the DLT evaluation, and the safety and tolerability must be reviewed by the SRC before the first subject in the next dose group can receive the first dose.

Subject Replacement: During the DLT evaluation period, if a subject is unable to be evaluated for DLT (e.g., the subject's dose of the study drug did not reach at least 80% of the protocol-specified dose, or the subject discontinued study treatment before completing the DLT evaluation period for reasons other than DLT), additional subjects will need to be enrolled to make up the corresponding number in that dose

group.

DLT Definition: This study will grade toxicities according to NCI CTCAE v5.0. DLT refers to the following toxicity reactions that are considered by the investigator and/or the sponsor to be definitely or possibly related to the study drug CNSI-Fe, occurring within the first cycle (i.e., within 21 days after the first dose):

Hematological toxicity:

- (1) Any grade 4 hematological toxicity;

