The baseline imaging evaluation will be performed within 28 days prior to the first study treatment (if the subject has undergone imaging examinations at the study site during the routine clinical care process prior to signing the ICF, and the examination site and method meet the protocol requirements, and the examination time is within 28 days prior to the first study treatment, the corresponding examination results may be used for this trial's screening after the investigator's consent).

All subjects will undergo tumor assessment once every 3-4 weeks during the study treatment period, and once every 7-8 weeks for those who enter the maintenance treatment period (the investigator may decide whether to perform additional imaging examinations for special changes in the disease condition, and the first tumor assessment must be performed at 3-4 weeks).

Subjects who achieve a complete response (CR) or partial response (PR) in the first assessment will require confirmation at least 4 weeks later.

The baseline tumor evaluation must include the chest, abdomen, pelvis, and head (to

exclude brain metastases), as well as other suspected tumor sites. Subsequent evaluations should re-evaluate all measurable and evaluable lesions found at baseline, including the chest, abdomen, pelvis, and other suspected tumor sites.

The imaging examination methods used for efficacy evaluation of subjects during the study period must be consistent with the baseline imaging evaluation methods.

Investigational medicinal products

The CNSI-Fe involved in this study is composed of a ferrous iron adsorbed carbon nanoparticle, which are prepared and used on-site. The drug information is as follows:

Drug Name	Dosage Form	Specification	Storage Conditions	Shelf Life
CNSI-Fe(II)	Injection	2 mL: 100 mg	Store at 2-8°C	24 months
Ferrous Sulfate for Injection Lyophilized	Powder for Injection	30 mg/vial (as ferrous)	Store at 2-8°C, protected from light	24 months

The carbon nanoparticle suspension injection and the ferrous sulfate injection are both provided by the applicant.

Packaging and labeling: The nano carbon suspension injection and the ferrous sulfate injection are labeled by the applicant according to the "Good Manufacturing Practice for Drugs (Revised in 2010)" (NMPA, 2011) and the "Good Clinical Practice for Drugs" (NMPA, 2020), and are marked as for clinical trial use only.

dosage regimen

Dose Escalation Phase (DLT Phase)

Dosing

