Three dose groups are tentatively set (calculated as Fe²⁺, 30 mg, 60 mg, 90 mg). If ≥ 2 subjects in the 90 mg group observe DLT, the dose will be reduced to 75 mg for safety and tolerability observation; if the dose is escalated to 90 mg and MTD is still not reached, the SRC will comprehensively discuss the available safety, tolerability, PK/PD, and preliminary efficacy data, and consider further dose escalation to 120 mg, 150 mg, or even higher (if 120 mg still does not reach MTD, the SRC will discuss whether to stop dose escalation or directly proceed to 150 mg or even higher doses).

Dosing Volume

Regardless of tumor size, number, and location, a single tumor lesion suitable for intratumoral injection will be selected, and the corresponding dose of the investigational drug will be administered by intratumoral injection. The dosing volume will be determined based on the size of the injected lesion. If the corresponding dose of the investigational drug cannot be fully administered in one lesion, other lesions can be injected simultaneously. When multiple lesions are injected, the amount allocated to each lesion should be proportional to the lesion size, or the investigator can evaluate an appropriate allocation.

During the study, the investigator may adjust the dosing regimen or add unplanned

doses based on the safety, efficacy, and PK/PD data of CNSI-Fe.

CNSI-Fe Preparation

Take a vial of ferrous sulfate injection, keep the aluminum cap and rubber stopper sealed, and only remove the plastic outer cap of the aluminum-plastic combination cap. Use a suitable syringe to slowly draw an appropriate amount of the nano-carbon suspension injection, and inject it into the vial containing ferrous sulfate. Mix the solution evenly. The CNSI-Fe preparation requires aseptic operation, shielding from air, and must be used within 6 hours after preparation at room temperature. See Appendix 5 in Chapter 15 for details.

Maintenance Treatment Period

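### In the dose-escalation phase the investigator alone may change the regimen or add unplanned doses; if that covers injections, a second one can fall inside the 21-day DLT window

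*Combined protocol and SAP*

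**What the plan says.** All references are to the protocol synopsis and the notes to Table 1-1.

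- **Dosage regimen, Dose Escalation Phase (DLT Phase), Dosing Volume.** The permission applies throughout the study and reads "the investigator may adjust the dosing regimen or add unplanned", where the word that follows is doses. The grounds given are the drug's safety, efficacy and PK/PD results. Neither the sponsor nor the SRC is named.
- **Study Period, Treatment Period (including DLT Evaluation Period).** The plan is "preferentially selecting 1 suitable lesion for injection, tentatively with 1 injection on Day 1", and "the dosing regimen may be adjusted by the sponsor and investigator based on the PK characteristics of this study". The maintenance text and the Table 1-1 notes repeat this joint, PK-based rule for the second injection.
- **Dosing, directly above Dosing Volume.** Levels beyond 90 mg belong to the SRC, which is to "consider further dose escalation to 120 mg, 150 mg, or even higher".
- **Enrollment Interval.** Every subject of a group must first finish the 21-day evaluation. The rule then reads: "the safety and tolerability must be reviewed by the SRC before the first subject in the next dose group can receive the first dose".
- **DLT Definition.** A DLT is a qualifying drug-related toxicity "occurring within the first cycle (i.e., within 21 days after the first dose").
- **Subject Replacement and the DLT analysis set.** A subject needs at least 80% of the assigned dose to be evaluable. No upper limit is given.
- **Follow-up Period and the Table 1-1 notes.** Safety follow-up and adverse event reporting run to 28 days past the last dose.

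**The concern.** This is a first-in-human 3+3 design. Its decisions rest on how many of 3 or 6 subjects have a DLT at a known dose in a fixed window. The Dosing Volume sentence is a stated permission, not a missing detail, and it conflicts with another rule for the same period.

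What is at stake depends on what the sentence covers:

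- **Dose levels.** The investigator alone could add a level, although the synopsis elsewhere gives that decision to the SRC.
- **Injections.** A subject could receive more than the assigned dose before completing their own DLT evaluation. A resulting DLT would be credited to the assigned level although more drug had been given. A toxicity from the later injection that starts after Day 21 would not enter the count. The first error makes a level look worse than it is; the second can make it look better.

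**Working it through.** **1. The two rules side by side.**

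| | Dosing Volume (DLT phase) | Treatment Period (DLT evaluation period) |
|---|---|---|
| Who decides | Investigator | Sponsor and investigator |
| Basis | Safety, efficacy, PK/PD | PK |
| What may change | Regimen, or unplanned doses | Regimen |
| SRC step | None named | None named |

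The maintenance text and the Table 1-1 notes follow the right-hand column, so Dosing Volume is the outlier.

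**2. What the wording can mean.**

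- *For injections:* in the Treatment Period text the regimen clause follows directly on the one-injection plan, so regimen there includes number and timing of injections. The synopsis also uses dose for a single administration, as in the two-dose maximum in its study-duration paragraph. The sentence stands under Dosing Volume, which describes how a subject is injected.
- *For dose levels:* the Dose Groups paragraph speaks of added doses and plainly means levels.

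The text does not settle it.

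**3. The plan's own dose ladder.** From the basis for dose selection, with 60 kg body weight: 0.5 × 60 = 30 mg; 1.0 × 60 = 60 mg; 1.5 × 60 = 90 mg. This reproduces the stated levels. The next level named after 90 mg is 120 mg.

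**4. Cumulative amount after one full extra injection in cycle 1** (2 × assigned dose):

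| Group | Cumulative | Next level | Ratio |
|---|---|---|---|
| 30 mg | 2 × 30 = 60 mg | 60 mg | 60/60 = 100% |
| 60 mg | 2 × 60 = 120 mg | 90 mg | 120/90 = 133% |
| 90 mg | 2 × 90 = 180 mg | 120 mg | 180/120 = 150% |

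These are amounts given over up to 21 days, not peak exposures. Each is 200% of the assigned dose. The subject would still be evaluable, since the only stated dose limit is the 80% floor.

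**5. DLT window left for the later injection** (21 minus the day given after the first dose). Day 7: 21 − 7 = 14 days. Day 14: 21 − 14 = 7 days. Only the DLT classification stops at Day 21. Adverse event follow-up continues for 28 days from the later injection.

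**6. Comparison with the planned schedule.** The maintenance injection also brings the total to 2 × the assigned dose, for example 60 mg in the 30 mg group. It comes only after the subject's own DLT evaluation, without unacceptable toxicity, and after a benefit-risk judgment. The totals in step 4 therefore do not separate the two cases. The timing does: an extra cycle 1 injection comes before the subject's DLT evaluation is complete.

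**The case against.** The strongest reply is that the sentence is about dose levels or the regimen in general. Its basis is evidence about the drug rather than one patient's course, and nearly the same basis appears where the synopsis discusses levels. It is not expressly limited to cycle 1, and the Treatment Period text is the more specific rule for the DLT period. This stands as a plausible reading. It does not remove the problem, because a sentence naming only the investigator then conflicts with the SRC's control of levels.

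Three stronger readings are tempting, and the documents do not support them.

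- *A later injection would be watched for less than 21 days.* It would not. Follow-up and adverse event reporting run to 28 days past the last dose, with a safety visit then. Only the DLT label ends at Day 21.
- *Only this sentence lets cumulative dose reach the next level before SRC review.* The planned maintenance injection can do so too, when an early subject in a cohort completes evaluation before the last one.
- *The joint rule has an SRC step and this one bypasses it.* Neither rule names the SRC. The difference is sponsor involvement, and the suspension criteria describe the SRC as made up of the sponsor and investigators, among others.

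The two-injection rat study (Days 1 and 4) also tempers the safety worry. It does not bear on which dose level a DLT is credited to.

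**Conclusion.** The conflict over who decides, and on what basis, is plain in the text and holds under either reading. The consequence for the DLT count is conditional: it arises only if the wording covers injections and an extra one is given in cycle 1. In that case the assigned level's count reflects twice the assigned dose (60, 120 or 180 mg cumulative in the three planned groups, assuming a full repeat), and toxicity starting after Day 21 falls outside the count. The documents give no frequency for extra injections, so the likelihood cannot be sized.

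The available text ends in the notes to Table 1-1. The body sections it refers to were not available and may define unplanned doses or limit the permission. With that caveat, this is a modest point held with medium confidence. It is worth correcting because the design depends on a known dose in a fixed window and the correction is cheap.

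**What to change.** Replace the Dosing Volume sentence with wording such as:

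*No individual subject receives an added injection before the Day 21 DLT evaluation. Any regimen change or added dose level is proposed jointly by the sponsor and investigator and takes effect, for a whole cohort, only after SRC review. The investigator may withhold or reduce a dose at once for a subject's safety.*

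Then align the regimen-adjustment wording in the Treatment Period text, the Maintenance Treatment Period text and the Table 1-1 notes. Otherwise those places would still allow a regimen change without the SRC, and the edit would create a new contradiction.

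The cost is a few matching wording edits and slightly less investigator flexibility. No subjects, visits or assessments are added, and immediate action to protect a subject remains possible.

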Adverse events (AEs), vital signs, physical examinations, laboratory tests, Eastern Cooperative Oncology Group (ECOG) performance status (see Appendix 1), 12-lead electrocardiogram (ECG), echocardiography, etc. during the study period; Incidence of dose-limiting toxicities (DLTs).

Secondary Endpoints:

Pharmacokinetics (PK)

Including but not limited to area under the curve (AUC_{0-t}), peak concentration (C_{max}), AUC_{0-∞}, time to peak concentration (T_{max}), apparent volume of distribution (V_d), elimination rate constant (K_e), half-life (t_{1/2}), apparent clearance (CL), mean residence time (MRT), Vd/bioavailability (F), CL/F, accumulation ratio, etc.

Efficacy

Evaluation of anti-tumor efficacy of the injected lesions based on the revised Response Evaluation Criteria in Solid Tumors version 1.1 (revised RECIST v1.1) (see Appendix 2), including objective response rate (ORR) and disease control rate (DCR); Evaluation of overall anti-tumor efficacy based on the Response Evaluation Criteria in Solid Tumors version 1.1 (RECIST v1.1) (see Appendix 3).

Note: The primary efficacy endpoints are ORR and DCR of the injected lesions based on the revised RECIST v1.1.

Exploratory Endpoints

Exploration of the levels of hydrogen peroxide (H_2O_2), peroxidase (POD), malondialdehyde (MDA), glutathione (GSH), glutathione peroxidase 4 (GPX4), hydroxyl radical ($\cdot OH$), etc. in tumor tissue samples after administration (optional);

Exploration of the intratumoral PK study in the injected lesions, if available (not mandatory);

Exploration of the dose-response relationship between tumor size and administered dose/concentration using three-dimensional reconstruction technology (3D-CTA) to guide rational dosing in future clinical trials (not mandatory).

Total number of subjects: up to 30 cases, the final sample size will depend on the number of dose groups evaluated and the tolerability in each dose group.

Number of study centers: expected to be 3-6 centers.

Subject Selection Criteria

Inclusion Criteria:

Patients must meet all of the following criteria to be eligible for enrollment:

Understand and voluntarily sign the written informed consent form (ICF), have the willingness and ability to comply with all trial requirements;

Signed the ICF and are male or female aged 18-80 years (inclusive) at the time of signing the ICF;

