Patients with histologically or cytologically confirmed advanced solid tumors, for whom standard treatment is ineffective (disease progression after treatment or unable to tolerate treatment) or there is no effective standard treatment available, such as colorectal cancer, pancreatic cancer, breast cancer, gastric cancer, cervical cancer, lung cancer, head and neck cancer, cholangiocarcinoma, renal cell carcinoma, prostate cancer, vulvar cancer, etc.

Note: Patients with advanced solid tumors who are unable to receive standard treatment due to any reason leading to disease progression, or patients with tumor types insensitive to current standard treatments (such as pancreatic cancer, undifferentiated thyroid cancer, and sarcoma) who have disease progression after receiving the first course of standard treatment, can be included.

According to RECIST v1.1, have at least one measurable lesion, and this lesion has not received prior radiation therapy (unless there is clear progression of the lesion

after radiation therapy), nor has it undergone a tissue biopsy within 7 days prior to the first dose;

Have an injectable lesion (e.g. can be directly injected or assisted by medical imaging instruments);

ECOG performance status of 0-1 within 7 days prior to the first dose;

Expected survival time \geq 12 weeks;

Drug-related adverse reactions (ADRs) from prior treatments have recovered to \leq Grade 1 per NCI CTCAE v5.0 (except for alopecia) prior to screening;

Left ventricular ejection fraction (LVEF) \geq 50%;

Within 7 days prior to the first dose, have adequate hematologic and end-organ function, with laboratory tests meeting the following criteria:

a) Hematology

No use of granulocyte colony-stimulating factor (G-CSF) within 14 days prior to hematologic laboratory tests, and absolute neutrophil count (ANC) \geq 1.5 \times 10⁹/L;

No platelet transfusion within 14 days prior to hematologic laboratory tests, and platelet count (PLT) \geq 90 \times 10⁹/L;

No blood transfusion or use of erythropoietin within 14 days prior to hematologic laboratory tests, and hemoglobin (Hb) \geq 90 g/L;

b) Renal function

Serum creatinine (Cr) \leq 1.5 \times upper limit of normal (ULN) or calculated creatinine clearance (Ccr) \geq 50 mL/min using the Cockcroft-Gault formula (only calculated if baseline Cr $>$ 1.5 \times ULN);

c) Hepatic function

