Before the first CNSI-Fe dose, within 21 days after the first CNSI-Fe dose (specific time points to be determined based on clinical practice).

Subject to the subject's willingness, try to collect tumor tissue samples from the injected lesion before and after the first CNSI-Fe dose; the pre-dose tumor tissue sample can be the most recent archived sample or the sample collected during the screening period; post-dose tumor tissue samples will be collected according to clinical practice as much as possible to complete the tumor PK study (not a mandatory requirement).

Statistical Analysis: Analysis of the Data Set

Full Analysis Set (FAS)

The FAS includes all enrolled subjects who received at least one dose of the study drug and had a measurable lesion at baseline.

Dose-Limiting Toxicity (DLT) Analysis Set (DLTS)

The DLTS includes subjects who completed the DLT evaluation period as per the protocol (defined as receiving at least one dose of the study drug at $\geq 80\%$ of the protocol-specified dose and did not prematurely discontinue or experience a DLT during the DLT evaluation period).

Safety Analysis Set (SS)

The SS includes all subjects who received at least one dose of the study drug and had at least one post-dose safety assessment.

Pharmacokinetic (PK) Analysis Set (PKS)

The PKS includes all subjects who received at least one dose of the study drug and had at least one valid PK measurement.

Pharmacodynamic (PD) Analysis Set (PDS)

The PDS includes all subjects who received at least one dose of the study drug and had at least one valid PD endpoint measurement.

Statistical Analysis Methods

The Statistical Analysis Plan (SAP) will provide detailed specifications and descriptions of all planned statistical analyses in accordance with the protocol, and will be finalized prior to database lock.

The statistical analyses will include demographic and baseline characteristics, safety and tolerability, PK, PD, and efficacy.

The analyses will be primarily descriptive, without formal statistical hypothesis testing.

The statistical analyses will be performed using SAS® version 9.4 or higher.

The following descriptive statistical analyses will be conducted based on the nature of the variables:

Continuous variables: number of non-missing observations, mean and standard deviation (SD), median, minimum, and maximum.

Categorical variables: frequency and percentage.

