Safety Analysis: For the primary estimand, the number of subjects, incidence, and number of events of each type of adverse event will be summarized by dose group.

Numerical laboratory data at each visit will be described using mean, SD, median, extremes, and changes from baseline, and categorized as normal, clinically insignificant abnormal, or clinically significant abnormal, with the incidence of clinically significant abnormalities tabulated. The same approach will be used for ECG. Vital signs will be described using mean \pm SD.

For the secondary estimand, the incidence of DLTs will be summarized by dose

group.

PK Analysis: The primary PK endpoints for CNSI-Fe intratumoral injection will include the iron ion concentration in serum. PK analyses will provide descriptive statistics of the relevant measurements and concentration-time profiles. For the first dose of CNSI-Fe, AUC, Cmax, Tmax, and other parameters may be calculated. Descriptive statistics will be provided for these parameters, and informal testing of AUC may be performed to explore the relationship with dose.

Efficacy Analysis: Based on best lesion response, ORR, DCR, and their two-sided 95% confidence intervals (Clopper-Pearson method) will be statistically described.

PD Analysis: Descriptive statistics will be provided for the PD endpoint levels before and after dosing, as well as the changes (absolute or percent) from baseline. Corresponding time course profiles will be generated. Comparisons of the PD endpoint levels and changes from baseline at each timepoint will be performed, with normality testing and using paired t-tests or Wilcoxon signed-rank tests as appropriate.

Research on time:

After this study has been reviewed and approved by the Ethics Committee (EC), it

will continue until the expected sample size is reached, based on the actual situation.

The study is expected to end 28 days after the last participant receives a maximum of two doses. For participants who still achieve CR (complete response) or PR (partial response) at the end of the study, if the investigator determines that they can still benefit from continued treatment, they can receive the study drug free of charge until disease progression, development of intolerable toxicity, the investigator determines it is no longer appropriate for the participant to continue receiving the study drug, or the sponsor terminates the study.

Table 1-1. Clinical Trial Flow Diagram

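### Does the full analysis set let subjects without a measurable injected lesion into the injected-lesion ORR and DCR?

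*Combined protocol and SAP*

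**What the plan says.** The note under Secondary Endpoints, Efficacy, states: "The primary efficacy endpoints are ORR and DCR of the injected lesions based on the revised RECIST v1.1". Scoring follows the revised RECIST v1.1 in Appendix 2. Overall response by standard RECIST v1.1 is evaluated separately.

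The Inclusion Criteria contain two separate items. One requires that the patient "have at least one measurable lesion, and this lesion has not received prior radiation therapy" (with an exception for clear progression after radiotherapy), and that this lesion was not biopsied in the 7 days before the first dose. The next reads "Have an injectable lesion (e.g. can be directly injected or assisted by medical imaging instruments".

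The Study Period section chooses the lesion by "preferentially selecting 1 suitable lesion for injection". The Dosing Volume section bases volume on the size of the injected lesion and adds: "If the corresponding dose of the investigational drug cannot be fully administered in one lesion, other lesions can be injected simultaneously".

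Under Statistical Analysis, the FAS is defined as "The FAS includes all enrolled subjects who received at least one dose of the study drug and had a measurable lesion at baseline". The Efficacy Analysis paragraph gives the estimator, "Based on best lesion response, ORR, DCR, and their two-sided 95% confidence intervals (Clopper-Pearson method", without naming a set. Analyses are descriptive with no formal hypothesis test, and full specifications are left to a SAP to be finalized before database lock.

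**The concern.** The endpoint concerns one lesion, while the set that would supply its denominator is defined by a lesion that need not be the same one. A partial response is a percentage shrinkage, so a subject whose injected lesion had no usable baseline measurement may be unable to show one, although a complete response is not ruled out. Counting such a subject would pull ORR down for a reason unrelated to the drug. DCR could move either way, depending on how the subject was scored.

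The imaging section adds to the doubt: "Subsequent evaluations should re-evaluate all measurable and evaluable lesions found at baseline" implies that some lesions are not measurable. When several lesions are injected, the phrase about best lesion response also leaves open whether the unit is the subject or the lesion.

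Three things would be at stake. Dose cohorts have 3 to 6 subjects, so one subject moves a cohort proportion visibly. The study is open-label and the SAP can be finalized as late as just before database lock, so the denominator might be settled after responses are known. And the safety review committee may look at preliminary efficacy data when it discusses going beyond 90 mg.

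**Working it through.** **1. Does the text separate the two lesions?** It does not state that they are the same, and the two inclusion items are distinct. But other places point to one lesion:

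- The Sample collection section takes the exploratory tissue from the injected lesion. The notes to Table 1-1 describe the same samples as coming from the target lesion.
- Dosing Volume sets volume by the injected lesion's size and, by default, splits drug across several lesions in proportion to size. Injected lesions are therefore expected to be sized, although that is weaker than RECIST measurability.
- The measurable-lesion criterion limits biopsy of that lesion before the first dose, which is most natural if it is the lesion to be injected.

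The sentence on measurable and evaluable lesions concerns re-imaging everything found at baseline. It says nothing about which lesion is injected. The opening of Dosing Volume (a single suitable lesion, whatever the size, number and location) can be read as waiving a size condition or as fixing how many lesions are injected. It does not decide the point.

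**2. Is the denominator really open?** Five sets are defined: FAS, DLT, safety, PK and PD. Four have named uses outside efficacy. The FAS remains, and it is the only one with a tumor-measurement condition. Since eligibility already requires a measurable lesion, the FAS is in effect all treated eligible subjects. It is a set of subjects, and a Clopper-Pearson interval needs independent units, so one outcome per subject is the ordinary reading.

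**3. How much could the choice matter?** The plan states no ORR or DCR, so there is no figure to reproduce. The total of up to 30 subjects comes from the synopsis. Responder counts and the number *m* of subjects without a measurable injected lesion are assumptions. For *x* responders among *n*:

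- lower limit = Beta quantile at 0.025 with parameters (*x*, *n* − *x* + 1)
- upper limit = Beta quantile at 0.975 with parameters (*x* + 1, *n* − *x*)

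| Assumed case | FAS | Restricted |
|---|---|---|
| ORR, 6 responders, *m* = 1 | 6/30 = 20.0% (7.7–38.6) | 6/29 = 20.7% (8.0–39.7) |
| ORR, 6 responders, *m* = 3 | 6/30 = 20.0% (7.7–38.6) | 6/27 = 22.2% (8.6–42.3) |
| ORR, 6 responders, *m* = 9 | 6/30 = 20.0% (7.7–38.6) | 6/21 = 28.6% (11.3–52.2) |
| ORR, cohort of 6, *m* = 1 | 2/6 = 33.3% (4.3–77.7) | 2/5 = 40.0% (5.3–85.3) |
| DCR, cohort of 6, subject not controlled | 4/6 = 66.7% (22.3–95.7) | 4/5 = 80.0% (28.4–99.5) |
| DCR, cohort of 6, subject controlled | 5/6 = 83.3% (35.9–99.6) | 4/5 = 80.0% (28.4–99.5) |

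The pooled FAS interval is 38.6 − 7.7 = 30.9 points wide. One to three affected subjects shift ORR by 0.7 to 2.2 points. Even an extreme nine of 30 shifts it by 8.6 points, still within that interval. In a cohort of 6 the ORR shift is 6.7 points within an interval of 77.7 − 4.3 = 73.4 points.

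**4. Is the restricted denominator better?** If the removed subjects are all non-responders, ORR is multiplied by *n*/(*n* − *m*), so it can only rise. If one of the six responders had a complete response in a non-measurable injected lesion, restriction would discard it: 5/29 = 17.2% instead of 6/30 = 20.0%. The FAS figure is conservative for ORR in the first case and keeps a real response in the second.

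**The case for a change.** The strongest reply is that this is the named main efficacy measure, and that naming the FAS would not close the gap, because the FAS condition is met by any measurable lesion. The signs that the two lesions coincide are indirect and none is a selection rule. The remedy would cost little: a sentence and a flag derived from records already held. With open-label data, an earlier decision is better than a later one.

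Part of this stands. The available text does not say that the injected lesion must be measurable, and a cross-reference to Appendix 2 would be tidy. But the available text stops within the notes to Table 1-1 and does not include Appendix 2, to which the plan assigns the scoring of injected lesions. Silence here does not show that the rule is missing.

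The concern about timing is fair in principle, but the natural denominator keeps every treated eligible subject, which leaves little room for a favorable choice. The cohort-level shifts also assume that ORR and DCR are tabulated by dose group. The secondary objective speaks of different doses, but the analysis section prescribes dose-group summaries for adverse events and DLTs only.

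**Conclusion.** No change to the plan follows. The gap in wording is real, but it is one that analysts fill in the ordinary way: the FAS as denominator, one outcome per subject, and injected lesions combined as Appendix 2 directs. Listing any subject whose injected lesion was not measurable is routine in reporting and needs no new rule. Replacing the FAS with a restricted set would exchange a conservative ORR for a more favorable one and risk losing a complete response.

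Under the assumed counts, the pooled effect is 0.7 to 2.2 points for one to three affected subjects, against an interval about 31 points wide. It is zero if every injected lesion is measurable. ORR and DCR are secondary and descriptive. The 3+3 escalation rule and the MTD depend on DLTs alone. The safety review committee may consider preliminary efficacy when discussing doses above 90 mg, but no stated threshold on ORR or DCR governs that discussion.

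This rests on two assumptions: that few if any subjects have a non-measurable injected lesion, and that neither Appendix 2 nor the final SAP sets a conflicting rule. Neither could be checked in the text available.
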